10.5.6. Ophthalmoscopy and Optical Coherence

Subjects with a history of or active diabetic retinopathy, uveitis, retinitis pigmentosa or macular edema will be excluded from the study, as well as those with recent intraocular surgery.

A complete ophthalmoscopy and OCT assessment will be performed according to the Schedules of Assessments ([Appendix 1](#) and [Appendix 2](#)). The window to perform this testing is between Day -28 and Day -1 for the Screening Visit, -14 days for the Week 24 Visit, and \pm 10 days for all other post-screening visits.

A standard visual acuity chart should be used for the visual acuity assessment. The OCT machine used should preferably not be changed during the study to allow for comparison of central foveal thickness measurements within each subject across timepoints.

Screening Visit:

At the Screening Ophthalmology Visit, the eye examination will include:

- Ophthalmologic history
- Best corrected visual acuity measurement (autorefraction, using Snellen chart internationally)
- Ophthalmoscopy (may include contact lens biomicroscopy to examine the macula and optic disc)
- Measurement of central foveal thickness by OCT (recorded in micrometers; required for all subjects regardless of the results of visual acuity or ophthalmoscopy)
- Retinal photographs should be taken
- Ophthalmic findings should be recorded
- If there is a suspicion of macular edema by ophthalmoscopy and increased central foveal thickness by OCT, then a fluorescein angiography (FA) may be performed (at the discretion of the ophthalmologist). Subjects with diagnosed macular edema at Screening should be deemed a screening failure and should not be randomized

Scheduled Post-Screening Visits:

At the scheduled ophthalmology visit, the eye examination will include:

- Ophthalmic history
- Best corrected visual acuity measurement
- Ophthalmoscopy (may include contact lens biomicroscopy to examine the macula and optic disc)
- Measurement of central foveal thickness by OCT
- Retinal photographs should be taken
- Ophthalmic findings should be recorded

Subjects experiencing unexpected ophthalmic symptoms without a known suspected etiology or experiencing a relevant ophthalmic AE may need to have repeated ophthalmoscopy and OCT testing performed. Guidance on clinical monitoring of ophthalmic symptoms is provided in Section [10.5.7.7](#).

10.5.7. Safety Monitoring Guidance

10.5.7.1. Drug-Induced Liver Injury

Based on US FDA guidance for drug-induced liver injury ([FDA 2009](#)), discontinuation of study drug should be considered if any of the following occur:

- ALT or AST $> 8 \times$ ULN
- ALT or AST $> 5 \times$ ULN for > 2 weeks
- ALT or AST $> 3 \times$ ULN AND Total Bilirubin $> 2 \times$ ULN, or international normalized ratio > 1.5
- ALT or AST $> 3 \times$ ULN with the appearance of fatigue, nausea, vomiting, right upper quadrant pain or tenderness, fever, rash, and/or eosinophilia ($> 5\%$)

Information on the grading and management of laboratory abnormalities according to assessed severity is provided in [Appendix 4](#) and [Appendix 5](#).

10.5.7.2. Total WBC, WBC Differential, Lymphocyte Counts, and Infections

Etrasimod prevents lymphocyte egress from lymphoid tissues, resulting in a reduction in peripheral lymphocyte count and lymphocyte availability for recruitment to sites of inflammation. To minimize the risk of unintentional unblinding of treatment assignment, site staff including Investigators will be blinded to total white blood cell (WBC) count, WBC differential (percentage and absolute number), and lymphocyte subset results during the Double-Blind Treatment Period. Investigators should minimize review of WBC count and differential, and lymphocyte subset results obtained by other health care providers caring for study subjects when review of those data is not required to ensure the safety of study subjects.

In the Double-Blind Treatment Period, total WBC count, WBC differential, and lymphocyte subset results will be monitored by an IMM. The IMM will not be involved in any other aspects of study conduct or data analysis. If these laboratory values require follow-up during the Double-Blind Treatment Period, the IMM will notify the Investigator and provide instruction. Blinded values may be released to treating physicians and Investigators as deemed medically necessary.

The Investigator will not be blinded to laboratory results during the Open-Label Extension. Investigators should refer to [Appendix 5](#) for laboratory adverse events aside from ALC decreases.

ALC reduction is an on-target effect of etrasimod treatment. However, if ALC is confirmed below the 0.2×10^9 cells/L limit, study drug should be interrupted and should not be re-initiated if the ALC remains below this threshold. Investigators will repeat complete blood count with differentials weekly until $ALC > 0.5 \times 10^9$ cells/L. Re-initiation of the study drug should only be considered when $ALC > 0.5 \times 10^9$ cells/L. If a subject in the Open-Label Extension has a treatment interruption due to $ALC < 0.2 \times 10^9$ cells/L, then that subject may be re-initiated at 2 mg etrasimod and maintained for the rest of the Open-Label Extension without escalation to 3 mg etrasimod (Section [6.3.2](#)).

Refer to Section [10.5.7.3](#) for information on monitoring for signs and symptoms of infections and diagnostic work-up and treatment of infections.

10.5.7.3. Guidance on Monitoring Subjects for Infections

Reduction in peripheral lymphocyte count may have immunosuppressive effects. Low lymphocyte counts with the use of other S1P receptor modulators in patients with multiple sclerosis have been associated with serious and atypical infections ([GILENYA 2010](#), [MAYZENT 2019](#)).

To date, there have been no reports of PML with the use of etrasimod in clinical studies. Nevertheless, Investigators should remain vigilant in monitoring for signs and symptoms of serious and atypical infections during the study and after discontinuation of study drug (ie, the 4-week Follow-Up Period).

If a subject exhibits signs and symptoms suspicious for PML, study drug must be interrupted and cannot be restarted until diagnostic evaluation is completed and PML has been excluded. The Medical Monitor should be informed of any suspected cases of PML. Refer to [Appendix 6](#) for PML signs and symptoms and case evaluation algorithm. In the evaluation and management of treatment-emergent infections, Investigator may consult with infectious disease or relevant experts, as needed.

All radiologic images (eg, magnetic resonance imaging, computer tomography, X-rays) and diagnostic laboratory test results performed by local laboratories/facilities should be retained as source documents by study sites and made available upon request by the Sponsor for central adjudication as needed. All infections that develop during the study will be reported as AEs on the respective eCRF pages.

10.5.7.4. Guidance for Cardiac Monitoring Following Treatment Initiation or Re-Initiation

Cardiac monitoring following treatment initiation applies to both the Double-Blind Treatment (Day 1) and Open-Label Extension (Week 24) Periods. Cardiac monitoring may also be necessary to re-initiate study drug after dosing interruption (refer to [Section 6.3.2](#)).

Pre-randomization (ie, Baseline) and Week 24 predose vital signs (resting HR, BP, body temperature, and respiratory rate) will be used as the Baseline measurements for each respective visit. The lowest predose HR measurement will be used for comparison to the postdose measurement.

To minimize the risk of unintentional unblinding of treatment assignment, please refer to guidance regarding disclosure of HR data discussed in [Section 6.6](#).

First Dose Heart Rate Monitoring

In-clinic cardiac monitoring, of at least 4 hours following the first dose, will occur on Day 1, Week 24 and at treatment re-initiation and will include the following ([Table 6](#)):

- Full Baseline vital signs (HR, BP, body temperature, and respiratory rate) and 12-lead ECG will be assessed pre-randomization (ie, Baseline) for Day 1 and predose for Week 24.
- Holter monitoring will be performed as described in [Section 10.5.7.5](#).
- After the dose of study drug on Day 1 and, Week 24, and for the first dose when a subject re-initiates study drug, subjects must remain under direct observation in the clinic for at least 4 hours.
- At Hours 1, 2, and 3 (\pm 15 minutes) postdose, HR and BP will be assessed via vital signs with the subject in the seated position, with the time recorded. If the subject has an HR < 50 bpm, or if cardiovascular symptoms develop (eg, chest pain, dizziness, palpitations, and/or syncope associated with reduction of HR), the subject should

- remain closely monitored, including 12-lead ECGs as clinically indicated, until the Hour 4 discharge assessment.
- At the Hour 4 (\pm 15 minutes) discharge assessment, HR and BP will be assessed via vital signs with the subject in the seated position; a 12-lead ECG in the supine position will also be performed. Subjects may be discharged from the clinic after the 4-hour assessment if they meet the criteria described in Table 7. Subjects not meeting the discharge criteria will require extended monitoring as described below.
 - Subjects experiencing a clinically relevant treatment-related symptomatic event (eg, chest pain, dizziness, palpitations, and/or syncope) associated with reduction of HR together with clinically relevant 12-lead ECG changes at any time during the 4-hour monitoring period should be discontinued from study drug (Table 8).

Table 6: Procedures to be Performed During the Cardiac Monitoring Period

Procedure	Predose	Hours 1, 2, and 3 Postdose ^a	Hour 4 Postdose ^a
Blood pressure and heart rate ^b	X	X	X
12-lead electrocardiogram	X		X
Holter monitor ^c	X		
Assess discharge criteria			X

^a Measurements may be taken \pm 15 minutes of the scheduled time.

^b Heart rate is based on vital signs.

^c Monitoring from 15 minutes before dosing until Hour 8 (\pm 15 minutes) postdose (Section 10.5.7.5).

Table 7: Discharge Criteria After Cardiac Monitoring

Subjects will be released from the clinical site after dosing on Day 1 and Week 24 (but no sooner than 4 hours postdose) when they fulfill the following discharge criteria:
• Vital sign heart rate \geq 50 bpm
• If vital sign heart rate $<$ 50 bpm, then the decrease from Baseline must be $<$ 10 bpm
• No evidence from ECG of second-degree AV block or higher
• No patient-reported cardiac symptoms (eg, chest pain, dizziness, palpitations, lightheadedness, shortness of breath, or syncope)

Note: Subjects should have written instructions on when to return to the clinic and a 24-hour contact phone number to call in the event of any new or worsened cardiovascular symptoms.

AV, atrioventricular; bpm, beats per minute; ECG, electrocardiogram

Extended Cardiac Monitoring

Subjects who do not meet discharge criteria at 4 hours postdose will require extended cardiac monitoring:

- Vital signs will be assessed hourly and a 12-lead ECG may be performed, as clinically indicated, until the subject meets the discharge criteria (Table 7).
- The Medical Monitor should be contacted if the subject does not meet the discharge criteria after \geq 4 hours of extended cardiac monitoring.

- Any subject who requires extended monitoring must return the following day for the subsequent dose and will be re-monitored as on the previous day. These subjects will be discontinued from study drug if they do not meet the discharge criteria at 4 hours after the subsequent dose during re-monitoring. Extended cardiac monitoring should be continued until the subject meets the discharge criteria (Table 7).
- Subjects experiencing a symptomatic event (eg, chest pain, dizziness, palpitations, lightheadedness, shortness of breath, and/or syncope) at any time during the 4-hour monitoring period that is not associated with either a reduction in HR or clinically relevant change in 12-lead ECG, may be discharged provided they meet the discharge criteria (Table 7), as deemed appropriate by the Investigator; however, these subjects must return the following day for the subsequent dose and will be re-monitored as on the previous day. These subjects should be discontinued from treatment if they do not meet the discharge criteria at 4 hours after the subsequent dose during re-monitoring and extended cardiac monitoring should be continued until the subject meets the discharge criteria (Table 7).

Study Drug Discontinuation Related to Postdose Cardiac Monitoring

A complete list of reasons for study drug discontinuation is provided in Section 8.1. Reasons for study drug discontinuation specific to postdose cardiac monitoring are provided in Table 8. The Medical Monitor should be contacted before discontinuing a subject from study drug.

Table 8: Discontinuation of Study Drug Related to Postdose Cardiac Monitoring

Reasons for Study Drug Discontinuation Related to Postdose Cardiac Monitoring ^a

• Subjects who have a cardiovascular treatment-related symptomatic event (eg, chest pain, dizziness, palpitations, lightheadedness, shortness of breath, and/or syncope) associated with reduction of the HR or associated with clinically relevant 12-lead ECG changes at any time during the 4-hour monitoring period on Day 1 or Week 24 (or the following day during re-monitoring as applicable).

• Subjects who have not met the discharge criteria on Day 1 or Week 24 after ≥ 4 hours of extended monitoring, or the subsequent day during re-monitoring by 4 hours postdose.

^a All treatment discontinuations should be discussed with the Medical Monitor.

ECG, electrocardiogram; HR, heart rate

Cardiac Monitoring Upon Treatment Re-Initiation Following Dose Interruption

The procedure for first-dose cardiac monitoring as outlined should be performed and discussed with the Medical Monitor any time a subject misses study drug dosing as follows:

- ≥ 2 consecutive days within the first week of study drug during the Double-Blind Treatment Period and within the first week of study drug during the Open-Label Extension Period
- ≥ 7 consecutive days after the first week of study drug during the Double-Blind Treatment Period and after the first week of study drug during the Open-Label Extension Period

If these doses of study drug are missed, subjects must contact the Investigator to discuss treatment re-initiation and are required to return to the study site before taking their next dose of study drug at the study site.

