1.2. Benefit-Risk Considerations

As described in Section 1.1.1, modulation of the S1P/S1P receptor axis is thought to be a potential therapeutic approach to the management of a variety of immune-mediated disorders; as such, etrasimod may provide therapeutic benefit to patients with AA.

Etrasimod has been found to be safe and well-tolerated in subjects who have been dosed with the investigational drug. The safety and tolerability of etrasimod has been evaluated in Phase 1 studies with healthy adult subjects at single doses up to 5 mg and repeated doses up to 2 mg once daily without dose escalation and 4 mg once daily with dose escalation. Etrasimod has already demonstrated beneficial effects in another autoimmune inflammatory disease, UC.

While there have not been notable safety concerns with vital signs, electrocardiograms (ECGs), pulmonary function tests (PFTs), ophthalmoscopy, or laboratory test results with etrasimod, based on the mechanism of action of etrasimod and prior experience with S1P modulators fingolimod and siponimod, monitoring for these specific safety parameters is planned for this study. This monitoring includes PFTs, cardiac monitoring at first dose, when initiating 3 mg etrasimod, and on treatment re-initiation after a defined period of treatment interruption, liver function tests, and ophthalmoscopy with optical coherence tomography (OCT). Based on its mechanism of action, etrasimod is expected to dose-dependently reduce lymphocyte counts. This reduction is reversible, with lymphocyte counts returning to within normal limits following study drug discontinuation. Lymphocyte reduction may increase the risk of infections in some subjects. Any subject with a confirmed lymphocyte measurement $< 0.2 \times 10^9$ cells/L will be discontinued from study drug. Thus, serial assessment of white blood cell count and differential will be performed to assess the risk for serious and atypical infections, and study subjects will be closely monitored by Investigators.

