8. REMOVAL OF SUBJECTS FROM THERAPY OR ASSESSMENT

8.1. Discontinuation of Study Drug

Study drug *must* be discontinued in the following instances:

- Unacceptable AE or AE that, in the judgment of the Investigator, is considered to not be in the best interest of the subject to continue study drug
- Subject request to discontinue for any reason
- Pregnancy during the study (Section [10.5.9](#))
- Termination of the study by the Sponsor or at the request of a regulatory agency or an Institutional Review Board (IRB) or Independent Ethics Committee (IEC)
- Lost to follow-up
- Criteria met from cardiac HR monitoring to discontinue study drug (Section [10.5.7.4](#))
- Confirmed lymphocyte measurement $< 0.2 \times 10^9$ cells/L (Section [10.5.7.2](#))
- Received a prohibited concomitant medication that required discontinuation of study drug (Section [6.8.2](#))

- Other

Study drug *may* be discontinued in the following instances:

- Subject noncompliance
- Protocol deviation
- Drug-induced liver injury (Section 10.5.7.1)

Subjects who discontinue treatment prematurely, regardless of the reason, should be instructed to return for an ET visit within 1 week of when the last dose of study drug was taken, and for Safety Follow-Up Visits 2 weeks and 4 weeks after the last dose of study drug (ie, SFU 1 and SFU 2) (Appendix 1 and Appendix 2). If a subject fails to attend the follow-up visits, all reasonable efforts will be made to contact the subject to ensure that he/she is in satisfactory health. All contacts and contact attempts must be documented in the subject's medical record.

Whenever possible, subjects should continue on study and complete the remaining study visits and assessments even when study drug has been discontinued.

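### Three study-drug stopping rules (confirmed ALC below 0.2 × 10⁹/L, first-dose cardiac symptoms, failed extended cardiac monitoring) conflict between protocol sections

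*Protocol*

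**What the plan says.** **Lymphocyte count (ALC).** Section 8.1 lists the events at which study drug must be stopped. One is "Confirmed lymphocyte measurement" below 0.2 × 10⁹ cells/L, with a pointer to Section 10.5.7.2. Section 1.2 agrees: a subject with a confirmed count under 0.2 × 10⁹ "cells/L will be discontinued from study drug". Section 10.5.7.2 says that at the same limit "study drug should be interrupted and should not be re-initiated if the ALC remains below this threshold". It goes on: "Re-initiation of the study drug should only be considered when" the ALC is above 0.5 × 10⁹/L. For a subject interrupted in the Open-Label Extension, it adds "that subject may be re-initiated at 2 mg etrasimod and maintained for the rest of the Open-Label Extension without escalation" to 3 mg. It cites Section 6.3.2, whose general restart procedure takes 3 mg subjects back to 3 mg after one week on 2 mg and names no ALC exception.

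**First-dose cardiac symptoms.** Section 9.2.2 and the first-dose bullets of Section 10.5.7.4 name for discontinuation a subject whose symptoms come with both a fall in heart rate (HR) and relevant ECG changes. Both cite Table 8. Table 8 names a subject whose symptoms are "associated with reduction of the HR or associated with clinically relevant 12-lead ECG changes at any time during the 4-hour monitoring period".

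**Failed extended monitoring.** Table 8 also lists, as a reason to discontinue, failure to meet the discharge criteria on Day 1 or Week 24 after at least 4 hours of extended monitoring. The extended-monitoring bullets in the same section say to contact the Medical Monitor at that point. They then require any subject who needed extended monitoring to come back the next day for the following dose, and tie discontinuation to failure 4 hours after that dose.

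Section 8.1 makes stopping mandatory under "Criteria met from cardiac HR monitoring to discontinue study drug" and cites Section 10.5.7.4. Section 10.5.7.4 in turn describes Section 8.1 as the complete list of reasons.

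**The concern.** These rules protect subjects against expected, on-target drug effects, and the version followed can decide whether an affected subject receives another dose. A restart after a confirmed ALC below 0.2 × 10⁹/L complies with Section 10.5.7.2 and breaches the mandatory list in Section 8.1.

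Reporting is affected too. Section 8.1 attaches an early-termination visit to discontinuation, and the SAP summarises treatment discontinuation (Section 7.1), dose interruption (Section 9) and adverse events leading to study drug discontinuation (Section 11.1) separately. Because falls in lymphocytes and HR are drug effects, uneven application in the double-blind period would fall mainly on the active arms.

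**Working it through.** The plan gives no figure to reproduce. The check sets the texts side by side and follows one subject through each rule.

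**1. ALC.** Take a subject confirmed below 0.2 × 10⁹/L whose count later exceeds 0.5 × 10⁹/L.
- Sections 1.2 and 8.1: off study drug.
- Section 10.5.7.2: interrupted, and now eligible for a restart.

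Reading discontinuation as a temporary stop does not rescue this. The protocol treats interruption (Section 6.3.2, with a restart procedure) and discontinuation (Section 8.1, with an early-termination visit) as different things.

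**2. Cardiac symptoms.** For a subject with a treatment-related symptomatic event there are 2 × 2 = 4 combinations:

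| HR reduction | ECG change | Text of 9.2.2 and 10.5.7.4 | Table 8 |
|---|---|---|---|
| yes | yes | discontinue | discontinue |
| yes | no | not named | discontinue |
| no | yes | not named | discontinue |
| no | no | may be discharged if criteria are met; re-monitored next day | not listed |

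The text triggers stopping in 1 of 4 combinations and Table 8 in 3 of 4, so they differ in 3 − 1 = 2. The bullet in Section 10.5.7.4 on symptoms without either finding covers only the last row.

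The difference can become a direct clash. Take a subject with HR reduction only who still has symptoms at Hour 4. Table 7 requires the absence of cardiac symptoms for discharge, so this subject goes to extended monitoring. The extended-monitoring text then requires a return for the next dose. Table 8 lists the same subject for discontinuation.

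**3. Failed extended monitoring.** The conflict arises at 4 h + at least 4 h = 8 h or more after the dose. For a subject still failing the discharge criteria then:
- Table 8: a reason to discontinue. It is joined by *or* to next-day failure, so it is sufficient alone.
- Text of Section 10.5.7.4: contact the Medical Monitor; return next day for the following dose; discontinue if that dose also fails at 4 hours.

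**4. Which section governs.** Sections 8.1 and 10.5.7.4 refer to each other, so neither settles the cardiac rules. Section 8.1 points to 10.5.7.2 for ALC, but 10.5.7.2 points to 6.3.2 and not back. Section 9.2.2 cites Table 8 one way. The third conflict lies wholly inside Section 10.5.7.4.

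**5. Subjects exposed to the ALC rule.** Planned etrasimod subjects in the double-blind period: 24 (Cohort 1, 2 mg) + 24 (Cohort 2, 3 mg) + 6 (Cohort 2, 2 mg) = 54 of 78. In the Open-Label Extension everyone takes etrasimod: 78 × 0.85 = 66.3, about 66, if the plan's 15% drop-out applies to both cohorts; at most 78 with no drop-out. These count subjects exposed to the rule. They do not estimate how many will trigger it.

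**The case against.** The best defence concerns the two cardiac rules. The text on combined findings never says *only*; its case is a subset of Table 8's, and both sentences cite Table 8, so a site that applies both satisfies both. Section 8.1 also lets the investigator stop the drug on judgment for any adverse event. On extended monitoring, contacting the Medical Monitor can be read as the step the protocol requires before any discontinuation, not as an alternative to it.

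Part of this stands. Sections 9.2.2 and 10.5.7.4 do not themselves order re-dosing of a subject with one finding. But the extended-monitoring bullet does so for the subject still symptomatic at Hour 4, and its requirement to return carries no exception for a subject already due to stop under Table 8. Calling the Medical Monitor does not cancel it.

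On ALC the conflict is not disputed, but oversight limits it. In the double-blind period sites are masked and an Independent Medical Monitor directs action; Section 6.6 points that monitor to Section 10.5.7.2. The practical exposure is therefore mainly in the Open-Label Extension, where "The Investigator will not be blinded to laboratory results during the Open-Label Extension". Even in the double-blind period, the site still holds a mandatory list that says something else.

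The mismatch with Section 6.3.2 is secondary: the ALC text can be read as a specific exception to a general procedure. Few cardiac cases are likely, since Section 1.2 reports no first-dose symptomatic bradycardia with etrasimod and only rare AV block without symptoms.

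**Conclusion.** The concern holds. All three conflicts are in the current text, and as written the rules cannot all be followed. The ALC conflict is a plain contradiction. The symptom rule differs in 2 of 4 combinations and becomes a direct clash for a subject who also fails discharge at Hour 4. The extended-monitoring rule contradicts itself within one section.

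The number of subjects affected cannot be estimated, because the documents give no event rates, and the exposure counts are only upper bounds. The point rests on the consequence for each affected subject: whether the drug is given again, and how the case is classified. Sample size and power are untouched.

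**What to change.** Reconcile the passages. The sponsor's safety physicians should decide each of the three rules and state it once, in identical terms, wherever it appears across Sections 1.2, 8.1, 9.2.2, 10.5.7.2 and 10.5.7.4, including Table 8. The cross-reference from Section 10.5.7.2 to Section 6.3.2 should be aligned at the same time, and sites should receive a clarification letter. No version is recommended here.

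The cost is one clarifying amendment and one letter, with no change to sample size, assessments or analysis.

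A separate, minor item could go into the same amendment: the sentence in Section 1.2 on excluding subjects with elevated liver enzymes should be reconciled with Exclusion Criterion 25, which joins the transaminase and bilirubin limits with *and*.
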